In this study, the placebo will consist of inactive tablets identical to the active treatment tablets. Treatment assignments (active drug versus placebo) will be randomized for each patient to the two treatment periods within each block. (see Section F.1.6 for details about the randomization process; the unblinded randomization schema is available to unblinded study team members in Appendix I.

This study is part of Early-Phase Pain Investigation Clinical Network (EPPIC-Net), under The Helping to End Addiction Long-termSM Initiative, or NIH HEAL InitiativeSM.

D. 2. Study Endpoints

D.2.1. Primary Safety Endpoint

The primary safety endpoint is the incidence of treatment emergent adverse events (TEAEs), reported between the administration of study drug on Day 1 and the completion of the study at Week 24 or Early Termination.

D.2.2. Primary Efficacy Endpoint

The primary efficacy endpoint is pain in the index knee, measured weekly using the WOMAC-A (Pain subscale), (Bellamy et al, 1988). We will use the numerical rating scale version of the WOMAC-A, with the subject assessing each of 5 questions using an 11-point (0 to 10) scale; the total score is the sum of the individual item scores (range 0-50). A higher WOMAC-A score represents worse symptom severity.

All WOMAC subscales show strong evidence of validity and reliability (Salafi et al, 2003), and are the most frequently used primary endpoints for OA trials because of their strong assay sensitivity (Jung et al, 2018). Assessments during the last 2 weeks of each treatment period will be used to test the primary hypotheses in order to avoid possible carryover effects of unknown duration. All weekly measurements of WOMAC-A will be used to study the course of OA pain symptoms during treatment, including onset of action and carryover effects.

D.2.3. Secondary Endpoints

The following measures are considered secondary outcomes related to pain due to OA of the knee. They will be assessed at Baseline and at study visits through Week 24. See Section F.1.1 Schedule of Events for full description of procedure timepoints. The Daily Knee Pain Intensity on a 0-10 NRS which will be recorded daily the week prior to each study visit. For a full description of secondary endpoint scales and assessments, see Section F.2.4 and F.2.5.

- Daily Knee Pain Intensity on a 0-10 Numeric Rating Scale (NRS).
- WOMAC-C (Function subscale)
- Hospital Anxiety and Depression Scale (HADS)

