F.2.3. Biobanking – Blood and Stool Repository for Future Use

The Informed Consent Form (ICF) will inform whether or not the subject has opted out of specimen biobanking. If the patient has opted out, no blood or stool sample for biobanking will be obtained.

F.2.3.1. Whole Blood (Baseline and End of Study)

The EPPIC-Net DCC's NYU Center for Biospecimen Research and Development (CBRD) will store and manage biological samples (biosamples) collected in this clinical trial. The samples will be used for the present study and also for potential future research as permitted by the study-specific informed consent form. Biosamples stored for this study may include, but are not limited to: whole blood, plasma, serum, stool, synovial fluid and/or derivatives of these specimens. The samples will be stored only for the period defined in the informed consent form, which may be indefinite. Biospecimens may be shared in accordance with the protocol-defined data and sample sharing plan and the informed consent form.

Biosamples will be documented in LabVantage, a secure network linking biospecimens to corresponding clinical and pathological data. LabVantage does not include any identifying personal health information (PHI). The CBRD and LabVantage meet all Good Laboratory Practice (GLP) and FDA guidelines.

F.2.4. Protocol Patient Measures

1. WOMAC-A (Pain subscale). Pain in the index knee, measured weekly by the WOMAC-A (Pain subscale). We will use the numerical rating scale version of the WOMAC, with the subject assessing each of 5 questions using an 11-point (0 to 10) scale, and the total index score is the sum of the individual item scores (range 0-50). A higher WOMAC-A pain score represents worse pain.

The WOMAC-A will be used to study the course of OA pain symptoms during treatment, including onset of action and carryover effects.

2. WOMAC-C (Function subscale). The WOMAC-C physical function subscale contains 17 items assessing daily functioning, each using an 11-point (0 to 10) numerical rating scale. The total index score (0-170) is the sum of the items. A higher WOMAC-C function score represents worse functioning and less ability to engage in daily activities.

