Should the subject decline to come into the site for an ET visit, an abbreviated version of the Week 24/ET visit should be performed over the telephone. Sites should complete as many as the patient is willing/able to complete remotely. If the subject is unable or unwilling to complete any of these assessments, it will not be considered a protocol deviation. The following assessments are listed in order of importance and should be completed in that order, dependent on the subject's willingness and capabilities:

1. WOMAC – A (pain scale)
2. WOMAC – C (functional scale)
3. Patient Global Impression of Change (PGIC)
4. Assessment of Analgesic Medication Use
5. Concomitant Medications and Therapies
6. Hospital Anxiety and Depression Scale (HADS)
7. Drug Compliance
8. Adverse Events
9. Pain Catastrophizing Scale – Short Form 6
10. PEG Scale
11. PROMIS Sleep Disturbance Scale – 6A
12. Sleep Duration Question
13. PROMIS Physical Functioning Short-Form 6b
14. Patient Health Questionnaire (PHQ)
15. Depression Generalized Anxiety Disorder – 2 item scale (GAD-2)
16. Tobacco, Alcohol, Prescription medication, and Other Substance use Tool (TAPS-1)
17. Opioid Use Questionnaire (OUQ)

The eCRF Completion Guidelines and MOP will provide further instructions on data collection for the end of study visits.

Failure to collect follow-up data despite best efforts will not be counted as a protocol deviation. Action items, instructions and script will be provided to site coordinators for tracking down and obtaining data from those patients who discontinued treatment. Logs will be kept for actions taken to reach each patient who discontinued treatment.

If a subject is lost to follow-up, every effort should be made to contact the subject by telephone. Two phone calls followed by a certified letter should be documented before considering the subject lost to follow-up.

For subjects who continue to be followed for safety, adverse events should continue to be reported as described in Section F.4.

F.3.3. Discontinuation of Study

This study may be suspended or discontinued in part or in whole, at any time. The study may be discontinued for a number of reasons, including but not limited to those listed below:

- Excessive AE(s) - serious [i.e., an SAE]
- It is determined that continuation in the study would be detrimental to subjects' well-being
- At the discretion of a study oversight body, such as NINDS, IRB, DSMB, etc.
- Loss of funding from the NIH

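### The fallback telephone early-termination list ranks adverse events eighth of 17, after 37 questionnaire items, so a call that ends early can miss recent non-serious events unknown to the site

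*Protocol*

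**What the plan says.** Protocol Section F.3.2 treats the telephone visit as a fallback. It first asks for a clinic end-of-study visit or, for patients who stop medication but keep their consent, for data collection up to the nearest of Weeks 6, 12, 18 or 24. The call replaces the Week 24/ET visit in one case: "Should the subject decline to come into the site for an ET visit". The ordering rule reads: "The following assessments are listed in order of importance and should be completed in that order", and the same sentence makes this depend on what the patient is willing and able to do. Of the 17 entries, the one at issue is "8. Adverse Events". On incomplete calls the section says: "If the subject is unable or unwilling to complete any of these assessments, it will not be considered a protocol deviation".

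Safety is half of the primary objective (protocol C.1, Aim 1; SAP 4.1.1). The primary safety endpoint is defined in two ways:

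- Protocol D.2.1 and SAP 4.4.1: incidence of treatment-emergent events from first dose to Week 24 or early exit.
- Protocol F.2.7: percentage of adverse and serious adverse events in the last two weeks of each treatment period. SAP Section 8 carries both definitions.

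**The concern.** The list is ranked explicitly by importance, yet WOMAC-C, PGIC and HADS, all secondary outcomes under Aim 3, stand above the assessment that feeds a primary objective. Patients who leave early and will not return to the clinic may well include those with tolerability problems. If such a patient tires of the call before the eighth entry, the events since the last contact are not asked about, and no deviation marks the gap. The loss could be informative: it would lower the event count on whichever treatment leads people to leave.

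Two features of the protocol add weight. Section F.3.1.1 sends patients who meet the automatic stopping criteria out through F.3.2, the section that holds this list. Section F.3.3.1(b) acts on as few as two patients with related Grade 3 or 4 events, so a single missed non-serious Grade 3 event could bear on that rule.

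**Working it through.** **1. What stands ahead of adverse events.** Item counts are from protocol F.2.4 for WOMAC-A ("with the subject assessing each of 5 questions using an 11-point (0 to 10) scale"), WOMAC-C ("The WOMAC-C physical function subscale contains 17 items assessing daily functioning") and HADS, and from SAP 4.4.3 for PGIC.

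| Rank | Assessment | Questionnaire items | Role |
|---|---|---|---|
| 1 | WOMAC-A | 5 | primary efficacy |
| 2 | WOMAC-C | 17 | secondary |
| 3 | PGIC | 1 | secondary |
| 4 | Analgesic use | review | |
| 5 | Concomitant medications | review | |
| 6 | HADS | 14 | secondary |
| 7 | Drug compliance | review | |
| 8 | Adverse events | | primary safety |

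Items before adverse events: 5 + 17 + 1 + 14 = 37. Items from secondary outcomes: 17 + 1 + 14 = 32. Entries ranked below adverse events: 17 − 8 = 9.

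**2. How many patients leave early.** The plan's completer figures reproduce: 55 × 0.85⁴ = 28.7 (SAP Section 6 gives about 29) and 50 × 0.85⁴ = 26.1 (protocol K.4 gives 26). Early leavers among 55 are therefore 55 − 28.7 = 26.3, or 48%.

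**3. How many could be affected.** Let p be the share of leavers who take the telephone visit and q the share of those calls that end before rank 8. The number affected is 26.3 × p × q. The documents give neither p nor q. Taking p as 10%, 25%, 50% or 100%, purely as an assumption, 2.6, 6.6, 13.1 or 26.3 patients would receive the call, and q then reduces each figure. Patients lost to follow-up never receive a call, so 26.3 is only a ceiling.

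**4. What each such patient could lose.** Adverse events are assessed at every visit (F.4.1), and visits are three weeks apart with a window of 4 days either way (Table 1). The exposed interval is nominally 21 days, and at most 21 + 4 + 4 = 29 days between consecutive attended visits. It is longer if a visit was missed.

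**5. Whether the lost events count.** Under the treatment-emergent definition they count whenever they occur. Under the last-two-weeks definition, an event in a patient who leaves during the first four weeks of a period may not count at all.

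**6. Comparison within the protocol.** For patients who cannot attend in extreme circumstances, F.1.2 has staff collect rescue medication, concomitant medications, adverse events and compliance by telephone or video, while the patient completes the questionnaires on a device. In that setting the questionnaires do not stand ahead of the adverse-event enquiry.

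**The case against.** A reader might infer that the order is mandatory and that staff must get through 37 items before they may ask about adverse events. The text does not support this. The verb is advisory, the order yields to the patient's willingness and capabilities, and any single assessment may be refused. A patient who declines WOMAC-C or HADS can still be asked about adverse events. The enquiry is missed only if the whole call ends before rank 8.

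A reader might also infer that adverse events are the data most easily lost from these patients. That is not so either: nine entries would be lost before them, and everything recorded at earlier visits is kept.

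There are other routes as well. F.4.8.1 requires every observed or reported event to be recorded, so one mentioned in passing during the call is captured. F.4.8.2 has serious events reported immediately. F.4.7.3 has patients withdrawn for an adverse event followed until it resolves or stabilises. F.3.2 continues event reporting for patients still followed for safety, and F.5 requires follow-up safety assessments to be completed as the protocol outlines. The site script, the completion guidelines and the manual of procedures are not available and may handle the question better than the list suggests. Aim 1 involves no hypothesis test.

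Most of this stands, and it narrows the point. It does not remove it. The non-specific adverse-event question belongs to visits, and this call takes the place of one. The serious-event and withdrawal routes work only once the site knows of the event. F.5 refers back to what the protocol outlines, and F.3.2 outlines non-completion without a deviation.

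**Conclusion.** The ranking is a real but modest design weakness. What is exposed is non-serious adverse events since the last visit, nominally three weeks, that the site does not yet know of, in early leavers who decline the clinic visit and whose call ends before the eighth entry. That is potentially informative under-ascertainment on a primary objective. The position (8 of 17) and the counts (37 items, 32 of them secondary) are exact.

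The number of patients is not established. The documents support about 26 early leavers at the planning rate of 15% per period and nothing finer, so any specific count of affected patients rests on assumed shares. The effect falls on descriptive rates, and its bearing on the endpoint depends on which of the two definitions applies. This is worth correcting because the correction is nearly free, not because a large loss has been shown.

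**What to change.** In F.3.2, move Adverse Events to first place, or to second place directly after the five-item WOMAC-A, and in either case ahead of WOMAC-C, PGIC and HADS. Then 0 or 5 questionnaire items precede it instead of 37. Align the telephone script and the related site instructions. The set of assessments, the sample size and the power are unchanged. The cost is one list edit and slightly more missing secondary questionnaire data from calls that end early.

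Separately, reconcile the two definitions of the primary safety endpoint (protocol D.2.1 and SAP 4.4.1 against protocol F.2.7, with both in SAP Section 8), and state whether events around an exit in the first four weeks of a period are counted.

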The PI will ensure the central IRB is provided with reports, updates, and other information (e.g., Safety Updates, Amendments, and Administrative Letters) according to regulatory requirements and institutional procedures.

A detailed list of required regulatory documents also to be submitted to EPPIC-Net Clinical Coordinating Center will be sent upon final approval of the protocol.

■ DATA HANDLING AND RECORDKEEPING

I.1. New England Survey Systems (NESS) NEForm

Radiology image uploads, radiology image review data, SAFER Rater data, electronic Patient Reported Outcomes (ePROs), and electronic Informed Consent (eConsent/eICF) will be collected using a validated electronic data capture system (NEForm by NESS). NEForm has been successfully deployed in Medical/Dental Operations as well as Clinical Trials. NEForm is fully validated and compliant to 21 CFR Part 11, HIPAA, GDPR, and other standards.

Data collected on the secure mobile application are stored locally on the mobile device, synced to a central server, and backed up on an off-location server. Data collected on the secure website are stored on a central server and backed up on an off-location server. Data collected are encrypted and uploaded/synced via additionally encrypted transmission to secure servers where access is limited according to the protocol. Strict operating procedures are enforced to protect the confidentiality, integrity, and access of Protected Health Information (PHI) when it is stored, transmitted, and maintained. When any PHI is collected in NEForm and uploaded to NESS, such PHI data are ONLY accessible to designated staff at NESS and handled in accordance with NESS SOPs. Such data are also only accessible to designated staff at the sponsor or the sponsor's designee when such access is properly requested. In such cases, the sponsor or sponsor's designee would follow their own SOPs.

The ePROs will be programmed by NESS and will include a notification system to patients reminding them to complete study activities. Data will be maintained by NESS and provided to the DCC at specific time points throughout the study. NESS will provide a dashboard that sites may access in order to ensure that patients are completing PROs at the appropriate timepoints. Sites are only able to see their own data. The DCC and CCC will be able to review all sites' data.

Additionally, automated and text message reminders will be sent by NESS to remind study patients about off-site ePROs, rescue medication use, and IP compliance.

For all data expected to be entered directly into NESS, paper source is permitted in the event of technical difficulties or other approved situational events.

I.2. Completion of EDC Forms

An Investigator is required to prepare and maintain adequate and accurate case histories designed to record all observations and other data pertinent to the investigation on each individual treated with the investigational product or entered as a control in the investigation.

TrialMaster will be used as the Electronic Data Capture (EDC) system and managed by the DCC. The EDC system will include eCRFs designed to capture study information, which are completed by trained site staff. Patient reported outcomes and additional eCRFs will be captured in the NESS EDC system. Data entered directly into the eCRFs via a tablet or other data entry device will be considered as source. Specific details of the procedures for Data Management are found in the Data Management Plan.

For all data expected to be entered directly into TrialMaster, paper source is permitted in the event of technical difficulties or other approved situational events.

I.3. Procedure for Corrections

Query resolution will be performed and tracked within the EDC system, and completed by trained site staff. Specific details regarding EDC query flow are found in the Data Management Plan.

I.4. Record Retention

The PI must retain investigational product disposition records, case report forms, and source documents for the minimum period required by applicable regulations and guidelines or institutional procedures, and at least for 10 years. If the PI withdraws from the study (e.g., relocation, retirement), the records shall be transferred to a mutually agreed upon designee (e.g., another investigator, IRB, EPPIC-Net). Notice of such transfer will be given in writing to the EPPIC-Net CCC and NINDS.

I.5. Data Confidentiality

Potential risks to data confidentiality will be mitigated by requirements for the de-identification of all study data and by security protocols for all data capture systems. All users of the EDC system will be tracked and provided access in a secure fashion following established Standard Operating Procedures (SOPs) for this process.

As with all research data, information gathered by the study will be used only for aggregate analysis; it will not be released with any information that identifies research Subjects. The data managers, statisticians, and PPI do not have access to the identities of patients. That information is retained only at the clinical sites. Uses and risks related to data collection will be outlined in the informed consent form and reviewed with the subjects.

I.5.1. Certificate of Confidentiality

This research is covered by a Certificate of Confidentiality (CoC) from the National Institutes of Health. The CoC protects subjects from the release or use of information, documents, or samples

without permission, including federal, state, or local civil, criminal, administrative, legislative, or other proceedings. An example would be a court subpoena. The CoC does not prevent the subjects from willingly releasing information about their involvement in this research.

■ MONITORING AND OVERSIGHT

Central IRB approval will be obtained and documented prior to subject enrollment and screening.

J.1. Evaluation of Study Sites

Potential study sites will be evaluated by EPPIC-Net to determine suitability for the proposed study. Information reviewed will include, but is not limited to, facility details and site capabilities, past performance in similar studies, investigator and staff experience, ongoing studies at the site, projected enrollment in this study, and FDA or other agency audit findings. Study sites may be asked to complete a study-specific Site Selection Questionnaire and other documents for consideration for participation and EPPIC-Net or clinical study monitors may make a Site Qualification Visit prior to completing the evaluation process. Upon completion of this evaluation, EPPIC-Net will invite the chosen sites for participation.

J.2. Initiation of Study Sites

Prior to subject enrollment, a study initiation visit will be completed at each investigational site to ensure the following: central IRB approval has been obtained and documented prior to subject screening, the investigators and study personnel are appropriately trained and clearly understand the study, the investigators and study personnel accept the obligations incurred in undertaking this clinical investigation.

J.3. Periodic Monitoring Visits

Qualified clinical monitors or qualified contract monitors representing EPPIC-Net will conduct investigational site monitoring visits to ensure that all investigators conduct the study in compliance with the protocol and applicable regulations. The site will receive notification prior to each monitoring visit during the course of the study. It is expected that the PI and/or Sub-Investigator(s) and other appropriately trained study staff are available on the day(s) of the visit in case any questions might arise.

Periodic monitoring visits will be made in accordance with the approved monitoring plan at all active study sites throughout the clinical study to assure that the PI obligations are fulfilled and all applicable regulations and guidelines are being followed. These visits will assure that the facilities are still acceptable, the protocol and investigational plan are being followed, the central IRB has been notified of approved protocol changes as required, complete records are being maintained, appropriate and timely reports have been made to the EPPIC-Net and the central IRB, and the PI is executing all agreed activities.

EPPIC-Net retains the right to remove either the PI or the investigational site from the study for issues of non-compliance with the protocol or regulatory requirements, in accordance with its SOPs.

On one or more occasions, the study site may be inspected or audited by an EPPIC-Net representative or a third party. The PI will be informed in advance of this visit.

J.4. Risk-Based Monitoring

EPPIC-Net will employ a protocol-specific Risk Based Monitoring (RBM) plan to ensure a robust quality control method for determining and enabling dynamic management of study risks and facilitating ongoing improvement in the trial conduct and oversight. The Acuity RBM system uses tools and dashboards to identify Key Risk Indicators (KRIs), which highlight potential issues with (for example) trial conduct, safety, data integrity, compliance, and enrollment, that may require further monitoring from a qualified contract monitor.

J.5. Suspension and Early Termination of a Site

The policies and procedures for the suspension or early termination of a study at a Clinical Study Site (i.e. Hub or Spoke participating in a particular clinical trial) are described in EPPIC-Net SOP Suspension and Early Termination of a Site. Circumstances that may necessitate invoking early termination or suspension of a site include but are not limited to:

- Enrollment at a site below expectation
- Protocol violations at the study site that place study subjects at risk of serious harm or that render the study data from that site untrustworthy or invalid
- Continuing or serious noncompliance by study investigators with regard to the protocol or regulations
- Any other site event that increases Subject risk of serious harm or undermines the integrity of the study
- Request of the site

The study can be suspended or terminated unilaterally at a site by the NIH, FDA, the central IRB, the local IRB (if applicable), or upon recommendation from the NINDS Data and Safety Monitoring Board (DSMB). The EPPIC-Net Study Trial Committee will receive concerns about site study suspension or termination, investigate, and determine if study should be suspended or terminated at a site, based on the above criteria.

J.6. Direct Access to Source Data/Documents

Subcontracts with study sites will specify that EPPIC-Net or its representatives will have direct access to source data and documents for study monitoring. Additionally, the central IRB, NINDS, and FDA may review source data following appropriate guidelines for this process.

J.7. Interim Analysis

No interim analysis is planned for this study.

J.8. Medical Monitoring

The Medical Monitor for this trial will be designated by EPPIC-Net. The Medical Monitor will review all adverse events, assess the benefits and risks of protocols on an ongoing basis, and work

in collaboration with the PPI to identify safety signals and trends, in accordance with the approved medical monitoring plan.

In addition, the Medical Monitor will be available to sites for questions regarding inclusion/exclusion criteria, protocol conduct, and safety. Trained and qualified EPPIC-Net staff physicians will be available to provide coverage during times when the Medical Monitor is unavailable. Sites will be provided with the Medical Monitor's cell phone number for emergency situations. Otherwise, sites are instructed to contact the Medical Monitor through email. Each month the Medical Monitor will receive a listing of protocol violations for review and identification of possible trends.

Serious adverse events will be reported to EPPIC-Net by the site within 24 hours of the site's knowledge of the event. In addition, the Medical Monitor may request individual patient records, including laboratory data, clinical records, and other study related data, to evaluate these events against the known safety profile of the study treatment and the disease. Any records sent to the Medical Monitor by the site will be redacted for any identifying information before transmission. The Medical Monitor may recommend actions including partial or complete unblinding, and/or modifying or terminating the study. In addition to safety monitoring, the Medical Monitor may review enrollment data, demographic information, retention status, and other reports prepared by the study statistician that describe study performance and progress.

J.8.1. Urgent Clinical Situations

During the course of the study, a patient will be reassessed for continued participation based on clinical judgment of the investigators. All subjects will be offered access to 24/7 coverage for medical emergencies through the clinical staff at each site. Treatment options and their risks and benefits, including continued study participation and other treatment options, will be sensitively explained. All study investigators have extensive clinical experience in the treatment knee OA, and can make the decision (while blinded) as to removal of subjects from the trial, particularly in the event of clinical deterioration. When a patient is removed from the trial based on clinical judgment, investigators will implement an appropriate treatment plan and arrange for follow-up for the patient.

J.9. The Data and Safety Monitoring Board (DSMB)

The NINDS DSMB will review the progress of the study and will monitor patient intake, outcomes, adverse events, and other issues related to patient safety. Interim, independent, and unbiased reviews of the study's ongoing progress will be provided. The DSMB will consist of experts in the study's subject matter field(s), clinical trials, biostatistics, and ethics. These individuals will not be Subjects in the trial and will not have participated in the planning of the protocol. The DSMB will consider safety or other circumstances as grounds for early termination, including either compelling internal or external evidence of treatment differences or the infeasibility of addressing the study hypothesis (e.g., poor patient intake, poor adherence to the protocol).

At each of its meetings during the study period, the DSMB will review the randomization rates and assess the difference between the actual and the projected rates, as well as the impact of these

assessments on overall trial size. If the study enrollment is inadequate, the reasons for exclusion may be scrutinized and actions may be suggested. An assessment of whether the trial should be continued will be made. The DSMB makes recommendations after each meeting to the NINDS Director about whether the study should continue or be stopped.

J.10. The Central IRB (Advarra)

The Central IRB will be the IRB of record for all sites. They will monitor the study's serious adverse events and review deviations on a continual basis. They will conduct annual reviews of the study.

■ DATA ANALYSIS

K.1. General statistical considerations

The general approach for inference for most of our aims will utilize a mixed-effects multi-period crossover model with 2 blocks and 2 treatment periods per block (of length 6 weeks). This model will be used to access the efficacy CNTX-6970 (300mg BID). Data will be analyzed on an intent-to-treat (ITT) basis with a per protocol analysis set used as a supportive analysis. Additionally, modified ITT (mITT) data sets will be prepared for supportive analyses to access the impact of the changes in the eligibility criteria across the different protocol versions.

In order to account for possible carryover effects, the multi-crossover model will incorporate carryover effect terms when appropriate. Only carryover effects from active to placebo will be formally tested, but a carryover effect from placebo to active will be studied in an exploratory fashion.

A patient who remains in the study for the first two treatment periods or for all four treatment periods will receive a balanced exposure to treatments randomized to receive. If patients discontinue treatment prior to completing the entire 24 weeks of study, all their data (including weekly assessments) from their time in the study will be used in the analyses. Because the main analysis is based on maximum likelihood estimation using a mixed-effects multi-period crossover model, the inferences will be unbiased under missing at random assumptions. No imputation of missing data is planned for this study, unless intensive investigations indicate that reliable and valid data imputation is possible, in which case multiple imputation will be performed and the analysis of the imputed data sets will serve as a sensitivity check of the results from the primary analysis based on the mixed-effects models (van Buuren et al, 2011).

All analyses will adjust for age, sex, K-L grade, and site.

All hypothesis tests will be two-sided using 5% significance level, and *p*-values unadjusted for multiple testing will be reported. The justification for this decision is that this is a Phase II investigation and all assessed outcomes are of specific and unique interest. Much more important than testing hypotheses is the efficient estimation of all quantities of interest, and this will be carried out throughout the analyses. Point estimates, 95% confidence intervals and standardized effect sizes (e.g., Cohen's *d*) will be reported for all estimated effects, regardless of whether the null hypotheses were rejected or not.

K.2. Hypothesis testing

Aim 1: Assess the safety of CNTX-6970 (300mg BID).

There will be no formal hypothesis testing under Primary Study Aim 1. All AEs and SAEs observed during different treatment periods will be summarized based on severity and relation to the active treatment (CNTX-6970 300mg BID). The reports will include tabulation of the AEs and SAEs by period, block, and treatment; point estimates and 95% CIs will be reported. Similarly, we will summarize relevant laboratory measures (see Section F.2.1) with appropriate estimates.

Aim 2: Assess the efficacy of CNTX-6970 (300mg BID) in comparison to placebo with respect to the primary outcome measure for pain due to osteoarthritis of the knee - WOMAC Part A.

WOMAC Part A (WOMAC-A) assessed only in the last two weeks of each 6-weeks treatment period will be used for this primary analysis in order to avoid any carryover effects, which are expected to vanish after 4 weeks; the specific carryover effect of the two doses of CNTX-6970 will be studied under Aim 3.

HYPOTHESIS 1: CNTX-6970 300mg BID is superior to placebo with respect to symptoms measured by WOMAC Part A.

The hypothesis testing is based on the WOMAC-A assessed only in the last 2 weeks of each 6-week treatment period. This provides a more than adequate 4-week washout interval. The adequacy of this 4-week period is based on extensive pharmacokinetics (PK) and pharmacodynamics (PD) of the study agent. The PK/PD analyses were performed for single dose and multiple ascending dose (MAD) studies using both QD and BID dosing regimens. For the single dose study, the PK study showed that the mean half-life ranged from 15.8 to 16.6 hours. For PD, the CNTX dossier reports that "... based on the half-life of CNTX-6970 determined in humans it is estimated that the duration of the PD may be between 8-12 hours." Specifically, after two doses of 300mg the plasma level is 10ng/ml 36 hours after dosing. The PD effect is less than 50% at 10ng/ml based on the MCP-1 interaction with CCR2. Hence, we anticipate a more than adequate washout period. Additionally, under Aim 6 (see below), we explicitly study the potential carryover effects in the statistical modeling. The statistical models will utilize a standard approach to adjust for carryover effects in a multi-period crossover design when estimating treatment effects, and allows for testing for the existence of carryover effect (Chen and Chen, 2014).

Aim 3: Assess the efficacy of CNTX-6970 (300mg BID) in comparison to placebo with respect to secondary outcome measures related to OA of the knee: (a) WOMAC-C (function subscale), (b) Hospital Anxiety and Depression Scale (HADS), (c) Patient Global Impression of Change (PGIC), (d) PROMIS Sleep Disturbance Scale – 6A, (e) Sleep Duration Question, and (f) Daily Knee Pain Intensity on a 0-10 NRS.

HYPOTHESIS 2: CNTX-6970 300mg BID is superior to placebo with respect to symptoms measured by (a) WOMAC-C (function subscale), (b) Hospital Anxiety and Depression Scale (HADS), (c) Patient Global Impression of Change (PGIC), (d) PROMIS Sleep Disturbance Scale– 6A, (e) Sleep Duration Question, and (f) Daily Knee Pain Intensity on a 0-10 NRS.

Outcomes (a) and (f) are assessed at baseline and each study visit through week 24. Outcome (b) will be assessed at each in-person visit except baseline. Outcome (c) will be assessed at week 3 and week 24 only. Outcome (d) will be assessed at baseline and each in-person visit through week 24. Outcome (e) will be assessed at baseline and week 24 only. The analysis plan for outcomes (a), (b), (d), and (f) will be similar to the analysis for aim 2 except that the model will adjust for possible carryover effects in placebo-treated periods that are preceded periods with the active drug treatment; the analysis plan for outcomes (c) and (e) will follow the same approach as in aim 4 below.

Aim 4: Assess the efficacy of CNTX-6970 (300mg BID) in comparison to placebo with respect to general outcomes of pain: (a) Pain Catastrophizing Scale –Short Form 6, (b) PROMIS Physical Functioning Short-Form 6b, (c) Patient Health Questionnaire (PHQ) – Depression, (d) Generalized Anxiety Disorder – 2 item scale (GAD-2); (e) Tobacco, Alcohol, Prescription medication, and other Substance use Tool (TAPS-1); and (f) Opioid Use Questionnaire.

HYPOTHESIS 3: CNTX-6970 300mg BID is superior to placebo with respect to outcomes measured by (a) Pain Catastrophizing Scale –Short Form 6, (b) PROMIS Physical Functioning Short-Form 6b, (c) Patient Health Questionnaire (PHQ) – Depression, (d) Generalized Anxiety Disorder – 2 item scale (GAD-2), (e) Tobacco, Alcohol, Prescription medication, and other Substance use Tool (TAPS-1), and (f) Opioid Use Questionnaire.

Outcomes (a)-(f) are assessed at baseline and week 24. Testing hypotheses for these outcomes will not benefit from the multi-period crossover design because they are assessed only at baseline and week 24. Instead, we will test the hypotheses by comparing subjects taking active drug versus placebo at the last treatment period ending on week 24, controlling for the baseline value of the outcome.

Aim 5: Assess the efficacy of CNTX-6970 (300mg BID) in comparison to placebo with respect to biomarkers of pain and inflammation: (a) Staircase-Evoked Pain Assessment, (b) Serum and synovial fluid levels of chemokines and cytokines; and (c) Synovial monocyte chemoattractant protein-1/CCR-2 receptor binding inhibition in blood and synovial fluid.

